Abbreviations: C=cycle; D=day; wks= weeks. For abbreviations on lab tests refer back to [Section 9.4.1](#).

Notes: Some of the assessments referred to in this section may not be captured as data in the eCRF. They are intended to be used as safety monitoring by the treating physician. Additional testing or assessments may be performed as clinically necessary or where required by institutional or local regulations.

^a If a dose is delayed, the procedures scheduled for that same timepoint should also be delayed to coincide with when that timepoint’s dosing actually occurs.

Table 2-4: On Treatment Procedural Outline for Arm C Sunitinib (CA2099ER)

Procedure	Cycle 1 Each Cycle=6wks		Cycle 2 ^a Each Cycle=6 wks		C3 and Subsequent visits ^a Each Cycle=6 wks		Notes
	Day 1	Day 22 (+/- 3 days)	Day 1	Day 22 (+/- 3 days)	Day 1	Day 22 (+/- 3 days)	
Safety Assessments							
Targeted Physical Examination, Vital Signs, Performance Status	X		X		X		Weight, BP, HR, RR, temperature, and Karnofsky Performance Status (KPS) (Appendix 7). Performance Status to be performed within 72 hours prior to dosing.
Assessment of Signs and Symptoms	X	X	X	X	X	X	
Adverse Events and Serious Adverse Events Assessment	X	X	X	X	X	X	Record at each visit. Participants will be followed for drug-related toxicities until these toxicities resolve, return to baseline, or are deemed irreversible. All adverse events will be documented for a minimum of 100 days after last dose (Appendix 3).
[REDACTED]	■	■	■	■	■	■	[REDACTED]
Electrocardiogram (ECG)	X		X		X (See notes)		Fridericia corrected QT (QTcF) required. Only Cycles 1, 2, and 3, then every 2 cycles (ie, Cycles 5, 7, 9, etc). If any time there is an increase in QTcF interval to an absolute value > 500 msec, 2 additional ECGs must be performed each with intervals approximately 3 minutes apart.
Laboratory Tests (includes blood and urine samples)	X	X (See notes)	X	X (See notes)	X	X (See notes)	See Section 9.4.1 for additional details on tests required. Laboratory tests do not need to be repeated at C1D1 if performed within 14 days prior to first dose. After C1D1, within 72 hours prior to specified dosing day: 
 CBC w/differential on Day 1 and Day 22 (+/- 3 days) of each cycle

Table 2-4: On Treatment Procedural Outline for Arm C Sunitinib (CA2099ER)

Procedure	Cycle 1 Each Cycle=6wks		Cycle 2 ^a Each Cycle=6 wks		C3 and Subsequent visits ^a Each Cycle=6 wks		Notes

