	Day 1	Day 22 (+/- 3 days)	Day 1	Day 22 (+/- 3 days)	Day 1	Day 22 (+/- 3 days)	
Participant-Reported Outcomes							
[REDACTED]	■		■		■		[REDACTED]
[REDACTED]	■		■		■		[REDACTED]
Health Care Resource Utilization	X		X		X		See Section 9.9 .
Study Treatment							
Randomize	X						Begins with call to Interactive Response Technology (IRT). Participants must have an evaluable PD-L1 result from the central lab in order to be randomized.
Administer Sunitinib	X	X	X	X	X	X	Day 1 Treatment must begin within 3 days (72 hours) of Randomization) Each cycle will be 6 weeks where sunitinib will be administered for 4 weeks, then participants will be off treatment for 2 weeks. See Section 7 .
Dispense Study Treatment	X		X		X		See Section 7 .

Abbreviations: C=cycle; D=day; wks= weeks. For abbreviations on lab tests refer back to [Section 9.4.1](#).

Notes: Some of the assessments referred to in this section may not be captured as data in the eCRF. They are intended to be used as safety monitoring by the treating physician. Additional testing or assessments may be performed as clinically necessary or where required by institutional or local regulations.

^a If a dose is delayed, the procedures scheduled for that same timepoint should also be delayed to coincide with when that timepoint’s dosing actually occurs.

Table 2-5: Follow-Up Procedural Outline for All Arms (CA2099ER)

Procedure	Safety Follow-up (Follow up Visit 1 (FU1) and Visit 2 (FU2) ^a	Survival Follow-up ^b	Notes
Safety Assessments			
Targeted Physical Examination, Vital Signs, Performance Status	X		Weight, BP, HR, RR, temperature, and Karnofsky Performance Status (KPS) (Appendix 7).
Assessment of Signs and Symptoms	X		
Adverse Events and Serious Adverse Events Assessment	X		Record at each visit. Participants will be followed for drug-related toxicities until these toxicities resolve, return to baseline, or are deemed irreversible. All adverse events will be documented for a minimum of 100 days after last dose (Appendix 3).
████████████████████	█		████████████████████
Electrocardiogram (ECG)	X		Fridericia corrected QT (QTcF) required. If any time there is an increase in QTcF interval to an absolute value > 500 msec, 2 additional ECGs must be performed each with intervals approximately 3 minutes apart.

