7.4.1.2 Dose Delay Criteria for Cabozantinib

Cabozantinib dosing should be delayed for the following:

- Urine protein/creatinine ratio (UPCR) > 2.0 *or* urine dipstick protein \geq 3+ *or* urine protein > 2.0 g / 24 hours. Obtain 24 hour urine protein prior to next dosing visit.
- Grade 3 prolonged QTc interval (ie, QTcF interval > 500 msec on at least 2 out of 3 separate ECGs performed at least 3 minutes apart)
- Any Grade 2 or 3 drug-related venous thrombosis requiring anticoagulation, with the following exception:
 - Any recurrent or worsening venous thromboembolic event after restarting cabozantinib will require discontinuation
- Any other Grade 2 drug-related adverse event or grade 2 drug-related laboratory abnormality (e.g., AST, ALT, total bilirubin) that persists for more than 1 week or worsens despite supportive care management, with the following exception:
 - Any Grade 2 drug-related hemorrhage requires dose delay
 - Grade \geq 2 arterial thromboembolic events, including cerebrovascular ischemia, cardiac ischemia/infarction, peripheral or visceral arterial ischemia, require discontinuation
- Sustained Grade 3 drug-related hypertension (systolic BP \geq 160 mm Hg or diastolic BP \geq 100 mm Hg). NOTE: Stopping or reducing the dose of cabozantinib is expected to cause a decrease in BP. The treating physician should monitor the participant for hypotension and adjust the number and dose of antihypertensive medications accordingly.
- Any other Grade 3 drug-related adverse event or laboratory abnormality, with the following exceptions:
 - Grade \geq 3 drug-related hemorrhage requires discontinuation ([Section 8.1.2](#)).
 - Drug-related AST or ALT > 8 x ULN requires discontinuation ([Section 8.1.2](#)).
 - Concurrent AST or ALT > 3 x ULN and total bilirubin > 2 x ULN, consistent with potential drug-induced liver injury (see [Section 9.2.7](#)), requires discontinuation ([Section 8.1.2](#))
 - Grade 3 drug-related amylase or lipase abnormalities that are not associated with symptoms or clinical manifestations of pancreatitis do not require dose delay. In such cases, more frequent monitoring (eg, weekly) of amylase and lipase is recommended. If amylase or lipase worsen to Grade 4 severity or the participant develops symptoms or clinical manifestations of pancreatitis, dosing should be delayed.

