7.4.1.3 Dose Delay Criteria for Sunitinib

Sunitinib dose delays should be based on instructions in the approved product label and should be considered for any severe or intolerable drug-related adverse events.

Within a cycle, missed doses of sunitinib should be skipped. Participants should never be dosed during the 2-week off period of each 6-week cycle, even if treatment delays occurred earlier in the cycle and therapy is ready to be resumed. If treatment is delayed past the end of the 6-week cycle, the start of the next cycle should be delayed until treatment with sunitinib resumes.

Prior to resuming therapy after a dose delay, refer to [Section 7.4.2](#) for dose reduction recommendations and [Section 8](#) for discontinuation criteria.

For this protocol, sunitinib dosing should be delayed for any of the following:

- Urine protein/creatinine ratio (UPCR) ≥ 2.0 or urine dipstick protein $\geq 3+$ or urine protein ≥ 2.0 g / 24 hours. Obtain 24 hour urine protein prior to next dosing visit.
- Grade 3 prolonged QTc interval (ie, QTcF interval > 500 msec on at least 2 out of 3 separate ECGs performed at least 3 minutes apart)
- Any Grade 2 or 3 drug-related venous thrombosis requiring anticoagulation, with the following exception:
 - Any recurrent or worsening venous thromboembolic event after restarting sunitinib will require discontinuation
- Any other Grade 2 drug-related adverse event that persists or worsens despite supportive care management, with the following exception:
 - Any Grade 2 drug-related hemorrhage requires dose delay
 - Grade ≥ 2 arterial thromboembolic events, including cerebrovascular ischemia, cardiac ischemia/infarction, peripheral or visceral arterial ischemia, require discontinuation
- Grade 3 drug-related hypertension (systolic BP ≥ 160 mm Hg or diastolic BP ≥ 100 mm Hg). NOTE: Stopping or reducing the dose of sunitinib is expected to cause a decrease in BP. The

treating physician should monitor the participant for hypotension and adjust the number and dose of antihypertensive medications accordingly.

- Any other Grade 3 drug-related adverse event or laboratory abnormality, with the following exceptions:
 - Grade \geq 3 drug-related hemorrhage requires discontinuation (Section 8.1.2).
 - Drug-related AST or ALT $>$ 8 x ULN requires discontinuation (Section 8.1.2).

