 - Concurrent AST or ALT $>$ 3 x ULN and total bilirubin $>$ 2 x ULN, consistent with potential drug-induced liver injury (see Section 9.2.7), requires discontinuation (Section 8.1.2)
 - Grade 3 drug-related amylase or lipase abnormalities that are not associated with symptoms or clinical manifestations of pancreatitis do not require dose delay. In such cases, more frequent monitoring (eg, weekly) of amylase and lipase is recommended. If amylase or lipase worsen to Grade 4 severity or the participant develops symptoms or clinical manifestations of pancreatitis, dosing should be delayed.
- Grade 4 drug-related amylase or lipase abnormalities require dose delay. Participants should be monitored for development of symptoms or clinical manifestations of pancreatitis.
- Grade 4 drug-related electrolyte abnormalities require dose delay. Electrolyte correction with supplementation/appropriate management should be promptly initiated.
- Grade 4 drug-related neutropenia, lymphopenia, leukopenia, anemia, or thrombocytopenia
- Any adverse event, laboratory abnormality, or intercurrent illness which, in the judgment of the investigator, warrants delaying sunitinib dosing
- For participants scheduled for major surgery, including dental surgery which may impact bone healing, sunitinib dosing should be delayed at least 28 days prior to scheduled surgery. The treating physician should use clinical judgment with regard to the risks and benefits of the planned surgical procedure if it is not possible to delay sunitinib dosing for 28 days prior to the procedure. A delay of sunitinib dosing of 5 to 7 days is recommended for healing for minor surgery.

As a general approach, all AEs related to sunitinib should be managed with supportive care when possible at the earliest signs of toxicity. Calcium, magnesium, potassium, and phosphorus should be kept above the lower limits of the laboratory normal values. Please refer to the sunitinib approved product label and Appendix 10 for additional information regarding AE monitoring and management.

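### Arm C has no visibly scheduled blood pressure on Days 2-28 of a sunitinib cycle, although the sunitinib delay rule rests on a BP threshold; a reading at the existing Day 22 visit would largely close the gap (minor)

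*Protocol*

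**What the plan says.** Protocol Table 2-4 lists BP by name in the notes to the row "Targeted Physical Examination, Vital Signs, Performance Status". That row is marked under Day 1 of Cycle 1, Cycle 2 and later cycles, and its Day 22 cells are blank. A Day 22 (+/- 3 days) visit does exist: the row "Assessment of Signs and Symptoms", the adverse event row, CBC and chemistry are all marked there.

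On dosing, Table 2-4 states: "Each cycle will be 6 weeks where sunitinib will be administered for 4 weeks, then participants will be off treatment for 2 weeks". Section 7.4.1.3 adds: "Participants should never be dosed during the 2-week off period of each 6-week cycle".

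The same section opens by basing sunitinib delays on the product label. It then lists delay criteria for this protocol, among them Grade 3 drug-related hypertension with the thresholds 160 systolic and 100 diastolic. A note to that bullet reads: "Stopping or reducing the dose of sunitinib is expected to cause a decrease in BP". The parallel cabozantinib bullet in Section 7.4.1.2 covers "Sustained Grade 3 drug-related hypertension". The sunitinib bullet has no such qualifier, so as worded one qualifying reading judged drug-related can engage it.

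Table 2-2 schedules BP at every 2-week cycle in Arm A, where cabozantinib is taken daily.

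**The concern.** The protocol sets a numeric BP threshold for delaying sunitinib, says BP should fall off drug, and then visibly schedules on-treatment BP only before the first dose or at the end of an off period. Asymptomatic hypertension during the four dosing weeks would then come to light only through a check that the schedule does not require. Section 8.1.3 also depends on BP, because it discontinues sunitinib for Grade 4 hypertension or for persistent Grade 3 hypertension despite management and dose reduction.

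The stake is first the safety of control-arm participants. The second stake is the hypertension comparison: adverse events are tabulated by arm and worst grade (Protocol 10.3.2, SAP 7.6.5), so unequal BP checking could affect it.

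**Working it through.** The check is a count of scheduled visits. It assumes dosing on schedule, takes the Week W visit as Day 7W + 1 (Week 24 = Day 169, Week 60 = Day 421), and includes the visit at the stated week.

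1. **On/off pattern.** SAP 7.4.1 gives a planned sunitinib intensity of 33.33 mg/day. 50 x 28 / 42 = 33.33, which confirms 28 days on and 14 off.

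2. **Drug-free gap before each later Day 1.** The last dose is on Day 28 and the next Day 1 is Day 43, so Days 29-42 are 14 drug-free days. Footnote a of Table 2-4 moves Day 1 procedures with a delayed dose, so the gap can lengthen but not shorten.

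3. **Post-baseline BP, Arm C.** Cycle k Day 1 = 1 + 42(k - 1).
   - By Day 169: Days 43, 85, 127, 169 = 4.
   - By Day 421: Cycles 2-11 = 10.
   - On cycle Days 2-28: 0.

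4. **Post-baseline BP, Arm A.** Cycle k Day 1 = 1 + 14(k - 1).
   - By Day 169: Cycles 2-13 = 12.
   - By Day 421: Cycles 2-31 = 30.
   - The first reading is on Day 15, against Day 43 in Arm C.

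5. **Dosing days without a scheduled BP.** Before Day 169, Arm C has 4 x 28 = 112 dosing days, of which 4 x 27 = 108 (96%) carry no scheduled BP. The same measure in Arm A gives 168 cabozantinib days with BP on 12 of them (Days 1, 15, ..., 155), leaving 156 of 168 (93%). The two percentages are close, so this measure does not separate the arms. What separates them is timing: each Arm A reading after Cycle 1 Day 1 falls during daily dosing, while each Arm C reading after Cycle 1 Day 1 follows an off period.

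6. **With BP added at Day 22.** Visits fall on 22 + 42(k - 1).
   - By Week 24: Days 22, 64, 106, 148 = 4 on-drug readings, total 4 + 4 = 8.
   - By Week 60: 10 on-drug readings (last on Day 400), total 10 + 10 = 20.
   - The window, Days 19-25, lies wholly inside dosing Days 1-28, after 18-24 doses if none is missed. It leaves 28 - 25 = 3 to 28 - 19 = 9 dosing days in that cycle.

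**The case against.** The strongest reply is that the protocol does not rely on the schedule alone.

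- **Label.** Section 7.4.1.3 puts the product label first for delays and refers to it again for adverse event monitoring. The label is not in the documents, so it cannot be judged whether it already asks sites for BP checks during dosing. This stands as a limit on the point.
- **Other routes.** The Table 2-4 notes say: "Additional testing or assessments may be performed as clinically necessary or where required by institutional or local regulations". Section 7.4.1.3 also allows delay for any event that, "in the judgment of the investigator, warrants delaying sunitinib dosing". Section 9.2.8 requires significant worsening on an unscheduled safety assessment to be recorded as an adverse event. These routes are real, but none is a scheduled reading. Weekly re-evaluation under Section 7.4.1 begins only once a delay is required.
- **Entry criterion.** Exclusion 1r removes poorly controlled hypertension (above 150/90). A participant can still enter 160 - 150 = 10 or 100 - 90 = 10 mm Hg below a delay threshold.
- **Redaction.** One redacted safety row in Table 2-4 is marked on Day 22. It is unlikely to be BP: BP is named in another row, and redacted rows in the same position in Tables 2-2, 2-3 and 2-5 sit in tables that also show a BP row.
- **Visit structure.** Arm A attends every 2 weeks for an infusion, and Arm C takes an oral drug in 6-week cycles. The 12 v 4 and 30 v 10 counts largely restate this.

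A reader might infer that no BP at all is scheduled on a sunitinib dosing day, or that the delay rule cannot be triggered. Neither follows. Day 1 is itself a dosing day, Grade 3 hypertension may still be present after the off period, and the rule also needs a judgment that the hypertension is drug-related, which can rest on an unscheduled reading.

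**Conclusion.** The gap is real but narrow. Table 2-4 visibly schedules no BP on cycle Days 2-28 in Arm C, so the protocol's own BP threshold has no scheduled reading taken after drug exposure within the cycle. This rests on the table as published, on the redacted Day 22 row not being BP, and on no BP schedule being imposed through the label.

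It might be inferred that the trial will under-count hypertension on sunitinib relative to the combination. The documents do not support that. They give neither size nor time course for the BP fall off drug, and other detection routes exist, so differential ascertainment is possible but not shown. The effect on the trial's conclusions is limited: safety is summarized descriptively (Protocol 10.3.2) and vital signs are only listed (SAP 7.6.11). Severity is minor: a cheap improvement in patient safety.

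**What to change.** In Table 2-4, add a BP reading under Day 22 (+/- 3 days) of every cycle and keep the Day 1 BP. No dose, delay or stopping rule needs to change.

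The cost is one extra reading per 6-week cycle at a visit that already takes place. The fix is partial. The early weeks of each cycle stay without a scheduled BP, Arm A keeps more readings (12 v 8 by Week 24, 30 v 20 by Week 60), and a Day 22 finding can affect only the last 3-9 dosing days of that cycle. It would still inform antihypertensive treatment and the dose of the next cycle.

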3 INTRODUCTION

Renal cell carcinoma (RCC) is the eighth most common cancer in the world with an increasing incidence.¹ Globally, RCC occurs in more than 330,000 cases with approximately a third of the patients succumbing to their disease. More than 100,000 deaths occur annually, as a result of progression of metastatic disease. Despite the earlier detection of smaller kidney tumors, the rate of RCC-related mortality has increased suggesting that recurrence and advanced disease are responsible for mortality.^{2,3} With the rise in RCC incidence, as well as mortality and morbidity associated with advanced RCC, medical need in this population remains a priority.

Over the last decade, an increased understanding of the biology of RCC has led to development of multiple agents that target specific growth pathways. The vascular endothelial growth factor (VEGF) pathway and targeted serine/threonine protein kinase therapies that block the mammalian target of rapamycin (mTOR) have been found to be important targets in RCC disease. Global health authorities (HAs) have approved multiple drugs targeting these pathways, including anti-VEGF agents, such as pazopanib, sorafenib, sunitinib, cabozantinib, and bevacizumab, and mTOR pathway inhibitors, such as temsirolimus and everolimus.⁴ Additionally, recent innovation of treating cancer with immunotherapies has also expanded treatment options. Nivolumab, an anti-PD-1 antibody, given as monotherapy or in combination with the anti-CTLA-4 antibody, ipilimumab, has demonstrated clinical activity in multiple tumor types, including RCC.

To better understand treatment and patient outcomes, several academic groups have identified variables associated with survival and created prognostic models in mRCC. These risk models are commonly used for choosing therapies or selecting patients for treatment in clinical trials. The International Metastatic Renal Cell Carcinoma Database Consortium (IMDC) model stratifies patients into 3 prognostic groups, based on 6 adverse prognostic factors, into favorable (0 factors), intermediate (1-2 factors), and poor risk (3-6 factors) groups.⁵ The currently available first-line agents for mRCC, which target the VEGF pathway, have shown limited efficacy in the intermediate and poor risk populations, yielding median overall survival of approximately 2 years or less.

Cabozantinib and nivolumab both share category 1 NCCN guideline recommendations (ie, uniform consensus that the treatment is appropriate, based on high-level evidence) for the treatment of previously treated mRCC patients.⁶ Therefore, it is an appropriate next step to combine these agents and move them to the first-line setting in an attempt to improve clinical outcomes in patients with advanced RCC. This protocol CA2099ER will test the clinical activity of nivolumab combined with cabozantinib (doublet regimen). Given the different mechanisms of action of each of these agents, there is potential for distinct improvement in clinical efficacy.⁷

[REDACTED]

[REDACTED]

[REDACTED]

[REDACTED]

3.1.1 Research Hypothesis

Treatment with nivolumab combined with cabozantinib (doublet regimen) will demonstrate an improvement in PFS per BICR compared to sunitinib monotherapy in participants with previously untreated mRCC.

4 OBJECTIVES AND ENDPOINTS

Table 4-1: Objectives and Endpoints

Objective	Endpoint
Primary	

To compare progression-free survival (PFS) per BICR of nivolumab combined with cabozantinib (Arm A: doublet) with sunitinib (Arm C) in all randomized participants.
	
The primary endpoint of this study is to compare PFS per BICR of Arm A versus Arm C in all randomized participants. PFS is defined as the time between the date of randomization and the first date of the documented progression, or death due to any cause, whichever occurs first. Participants who die without a reported progression (and die without start of subsequent anti-cancer therapy) will be considered to have progressed on the date of their death. Participants who did not progress or die will be censored on the date of their last evaluable tumor assessment on or prior to initiation of subsequent anti-cancer therapy. Participants who did not have any on study tumor assessments and did not die will be censored on their date of randomization. Participants who started anti-cancer therapy without a prior reported progression will be censored on the date of their last evaluable tumor assessment on or prior to the initiation of first subsequent anti-cancer therapy.

Secondary	

To compare overall survival (OS) of Arm A with Arm C in all randomized participants.
	
The first secondary endpoint is to compare OS of Arm A versus Arm C in all randomized participants. OS is defined as the time between the date of randomization and the date of death due to any cause. A participant who has not died will be censored at the last known alive date.


To evaluate the objective response rate (ORR) per BICR in all randomized participants.
	
The second secondary endpoint is to describe ORR per BICR in all randomized participants. ORR is defined as the proportion of randomized participants who achieve a best response of complete response (CR) or partial response (PR) using the RECIST 1.1 criteria. Best overall response (BOR) is defined as the best response designation recorded between the date of randomization and the date of objectively documented progression per RECIST 1.1 or the date of subsequent therapy (including tumor-directed radiotherapy and tumor-directed surgery), whichever occurs first. For participants without document progression or subsequent therapy, all available response designations will contribute to the BOR assessment. Duration of response (DOR) is defined as the time between the date of first confirmed documented response (CR or PR) to the date of first documented tumor progression (per RECIST 1.1) or death due to any cause, whichever occurs first. Participants who neither progress nor die will be censored on the date of their last tumor assessment. Responders who started anti-cancer therapy without a prior reported progression will be censored on the date of their last evaluable tumor assessment prior to the initiation of first subsequent anti-cancer therapy. Time to response (TTR) is defined as the time from randomization to the date of the first confirmed documented response (CR or PR), as assessed by BICR. DOR and TTR will be evaluated for responders (CR or PR) only.

Table 4-1: Objectives and Endpoints

Objective	Endpoint
To assess overall safety and tolerability in all treated participants.	As measured by the incidence of adverse events (AEs), serious adverse events (SAEs), AEs leading to discontinuation, deaths, laboratory abnormalities and changes from baseline.
[REDACTED]	[REDACTED]
[REDACTED]	[REDACTED]
[REDACTED]	[REDACTED]
[REDACTED]	[REDACTED]
[REDACTED]	[REDACTED]

